4.3.7. Length of stay in hospital

The length of stay in hospital over 90 days will be computed as the time from randomization to death or discharge disregarding the reason for the end of the hospitalization. A Cox regression model will then be fitted with this time as the response with an administrative censoring time set a 90 days from the day of randomization. The regression coefficient and associated standard error from the Cox regression model will be used to compute an estimate of the hazard ratio, along with a 95% confidence interval and a p-value. Kaplan-Meier estimates will be computed and plotted for the distribution of the time to the end of hospitalization for each arm of the study.

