1.6. Known potential benefits

Potential benefits of COVID-19 convalescent plasma (CCP) include improved survival, improvement in symptoms, decreased risk of intubation for mechanical ventilation, decreased risk of intensive care unit (ICU) admission, shortened hospitalization time and suppression of viral load.

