3. OVERALL DESIGN AND PLAN OF THE STUDY

3.1. Overview

Research Question – Does the transfusion of CCP collected from donors who have recovered from COVID-19 infection and who have detectable anti-SARS-CoV-2 antibodies reduce the risk of intubation or death at Day 30 in adults who are admitted to hospital with COVID-19 respiratory illness compared to standard of care?

Study Hypothesis - We hypothesize that treating hospitalized adult patients with COVID-19 respiratory illness will reduce the risk of intubation or death at Day 30. In addition, we hypothesize that other outcomes will be improved including risk of ICU admission, length of stay in ICU and length of stay in hospital.

Study Design: Multicentre open-label randomized controlled trial. An overview of the study design is included in the flow chart below.

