12.4.2. Secondary Endpoints

A cause-specific Cox regression model will be fitted for the intubation-free survival time defined as the first of the times of intubation or death with censoring at discharge or 30 days whichever comes first. A hazard ratio and 95% confidence interval will be computed from this fitted model.

Cumulative incidence functions will be estimated and plotted for each treatment arm for the time to intubation or death.

The restricted mean number of ventilator-free days over the first 30 days will be compared between the two groups based on a nonparametric tests.

The time to in-hospital death will be analyzed using a cause-specific Cox regression model treating the minimum of the time of discharge and 90 days as the censoring time. A hazard ratio and 95% confidence interval will be computed from this fitted model. Cumulative incidence functions will be estimated and plotted to estimate the proportion of patients who died during the initial hospitalization up to 90 days from randomization.

Finally, the survival status of individuals will be recorded at day 30 and the proportion of individuals who have died will be computed for each arm with a two-sample Wald test carried out based on the proportions.

Length of hospitalization over 90 days and length of stay in the ICU over 30 days will be modeled using a Cox regression without any distinction between reasons for discharge.

The proportion of patients needing ECMO over 30 days will be compared between the two arms based on a two-sided test of the difference between proportions.

The proportion of patients needing renal replacement therapy over the first 30 days will be compared between the two arms based on a Wald test.

The proportion of patients developing myocarditis over the first 30 days will be compared between the two arms based on a Wald test.

The change in EQ-5D-5L utility value from baseline will be compared between the two arms.

Incremental cost per quality-adjusted life year between the CCP and standard care over the 30-day time horizon.

No multiplicity adjustments will be implemented for the secondary analyses. Procedures for addressing missing data will be described in the SAP.

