1.3. Sample Size Justification

Assuming a 30% risk of the composite outcome of intubation or death by Day 30 among hospitalized patients under standard of care, a sample size of 1200 individuals (800 in the CCP arm, and 400 in the standard of care arm) will provide 80% power ($\beta = 0.20$) to detect a relative risk reduction of 25% with CCP therapy using a 2-tailed test at level $\alpha = 0.05$. We assume that no patient will be lost to follow-up.

2. Responses

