2.2.7. Length of stay in hospital

The number of days from randomization to the first event of death or discharge will be recorded as the length of stay in hospital. This time will be right-censored at 90 days to avoid the need to follow individuals who are hospitalized for a particularly long time until discharge; it is expected that most hospitalizations will not last beyond 90 days.

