4.3.4. Time to in-hospital death

The time to in-hospital death will be analyzed using a cause-specific Cox regression model to deal with the competing risks of discharge from the hospital in which the individual was randomized; for subjects hospitalized for more than 90 days their time of in-hospital death will be censored at 90 days. That is, individuals who did not die in the hospital they were admitted to at the time of randomization will have their follow-up censored at the time of discharge from this hospital. The regression coefficient and associated standard error from the cause-specific Cox regression model for death in the original hospital will be used to compute an estimate of the cause-specific hazard ratio along with a 95% confidence interval and a p-value. To accompany this analysis estimates of the cumulative incidence functions will be plotted for in-hospital death and discharge for each treatment group.

4.3.5. Death by Day 30

The probability of death between randomization and Day 30 will be estimated for each treatment group by the proportion of individuals randomized who died between randomization and Day 30. The test will be based on a 2-sided Wald test of the null hypothesis that the probability of death by Day 30 is the same among individuals receiving CCP or standard of care. The percent relative risk reduction will be estimated along with a 95% confidence interval and a p-value of the null hypothesis will be computed.

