4.3.12. Incremental cost per quality-adjusted life year (QALY)

In addition to the cost of CCP, we will estimate the cost associated with the stay in ICU, hospitalization, use of ventilator and ECMO, diagnostics and procedures, and medications. The difference in cost between CCP and standard care will be divided by the difference in QALY calculated using the EQ-5D-5L to derive the incremental cost per QALY for CCP. 95% confidence interval for the incremental ratio will be assessed using a non-parametric bootstrapping with replacement approach with B=1000 times.

4.3.13. CPP transfusion-associated adverse events at Day 30

Adverse events judged to be definitely or probably related to CPP will be analyzed two ways: 1) using the Common Terminology Criteria for Adverse events (CTCAE; Grading 1-5)); and using the ISBT definitions for acute transfusions reactions (Grades 1-4). (Protocol section 4.3.13),

1. CTCAE Grading: The proportion of individuals experiencing CPP transfusion-associated adverse events (CTCAE Grades 1-5) will be reported overall by type, and severity. The total number of CPP transfusion-associated adverse

events will also be tabulated overall by type, and severity which will accommodate the possibilities of multiple adverse events per individual.

2. ISBT Grading: The proportion of individuals experiencing CPP transfusion-associated adverse events (ISBT Grades 1-4) will be reported overall by type, and severity. The total number of CPP transfusion-associated adverse events will also be tabulated overall by type, and severity which will accommodate the possibilities of multiple adverse events per individual.

4.3.12. Grade 3, 4, and 5 adverse events at Day 30

See protocol section 9 for additional details regarding AE definitions.

The proportion of individuals experiencing Grade 3, 4 or 5 (as per CTCAE criteria) adverse events will be analyzed overall and by treatment arm by type, severity grade, and expected/unexpectedness. The total number of Grade 3, 4 or 5 adverse events will also be tabulated overall and by treatment arm by type, severity grade and expected/unexpected which will accommodate the possibilities of multiple events per individual.

4.3.13. Grade 3, 4 and 5 serious adverse events at Day 30

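### Hospital length of stay pools in-hospital death with discharge: a valid bed-use measure, but its hazard ratio cannot show faster recovery, and no live-discharge estimate is planned beside it

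*SAP*

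**What the plan says.** SAP 2.2.7 defines the outcome: "The number of days from randomization to the first event of death or discharge will be recorded as the length of stay in hospital", right-censored at 90 days. SAP 4.3.7 repeats that the stay is "computed as the time from randomization to death or discharge disregarding the reason for the end of the hospitalization", fits one Cox model, and reports a hazard ratio, 95% confidence interval and p-value with Kaplan-Meier curves. Protocol 12.4.2 agrees: hospital stay "will be modeled using a Cox regression without any distinction between reasons for discharge". The three places are consistent, so the pooling is deliberate.

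Protocol 1.6 counts "shortened hospitalization time" among the potential benefits. Protocol 3.1 hypothesises that "other outcomes will be improved including risk of ICU admission, length of stay in ICU and length of stay in hospital". Neither document says which direction of the pooled ratio is favourable.

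Two other passages bear on the point. SAP 4.3.4, on time to in-hospital death, treats discharge as a competing risk and says "estimates of the cumulative incidence functions will be plotted for in-hospital death and discharge for each treatment group". SAP 4.3.12 (cost per QALY) says "we will estimate the cost associated with the stay in ICU, hospitalization, use of ventilator and ECMO", so time in a bed is needed in its own right.

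**The concern.** A pooled ratio above 1 says only that patients left hospital sooner, alive or dead. If plasma both lowers mortality and speeds recovery, the two effects push the ratio in opposite directions. A listed secondary outcome, attached to a stated hypothesis of improvement, could then look null or adverse because the treatment works. If plasma raised mortality, the same outcome would drift in the direction the protocol calls a benefit. The curves in SAP 4.3.4 would show the discharge pattern, but without an effect estimate, interval or test. This point concerns hospital stay only; nothing is claimed about ICU days.

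**Working it through.** **Inputs from the documents.** 800 CCP and 400 standard-of-care patients; censoring at Day 90 for hospital stay; "Assuming a 30% risk of the composite outcome of intubation or death by Day 30 among hospitalized patients under standard of care" (SAP 1.3); a 25% planned relative reduction. The plan gives no figure for hospital stay to reproduce. Its sample size does reproduce: with 0.30 against 0.225, 400 and 800 patients, pooled variance and two-sided 0.05, power is 80.1%.

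**Inputs assumed, because the documents give none.** Constant exit rates totalling 0.10 per day in control. Share of control stays ending in death, s = 10% to 20%. Control deaths by Day 30 are s × (1 − exp(−3)), which is 9.5% to 19.0%. That lies inside the 30% assumed for intubation or death. A death-rate ratio of 0.75 borrows the planned 25% effect.

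**Formula.** Let D be the ratio of live-discharge rates and M the ratio of in-hospital death rates, CCP to control. With constant rates:

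pooled HR = (1 − s) × D + s × M

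Setting this to 1 gives the discharge gain that is exactly cancelled: D = 1 + s(1 − M)/(1 − s). With M = 0.75:

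- s = 10%: 1 + 0.025/0.90 = 1.028
- s = 15%: 1 + 0.0375/0.85 = 1.044
- s = 20%: 1 + 0.05/0.80 = 1.0625

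At s = 20% and D = 1.0625, the share of stays ending in death falls from 20% to 15% and the share ending in live discharge rises from 80% to 85%. The pooled ratio is 1.00 and the test rejects at about the 5% chance level.

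**Probability of significance.** Exits by Day 90 are 1 − exp(−9), so nearly all 1200 patients have the pooled event. The approximate z is ln(HR) × √(1200 × 1/3 × 2/3) = ln(HR) × 16.33, and the chance of significance in that direction is Φ(|z| − 1.96).

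| s | M | D | Pooled HR | z | Significant |
|---|---|---|---|---|---|
| 20% | 0.75 | 1.00 | 0.80 + 0.15 = 0.95 | −0.84 | 13%, longer |
| 20% | 0.75 | 1.10 | 0.88 + 0.15 = 1.03 | 0.48 | 7%, shorter |
| 10% | 0.75 | 1.10 | 0.99 + 0.075 = 1.065 | 1.03 | 18%, shorter |
| 20% | 1.50 | 1.00 | 0.80 + 0.30 = 1.10 | 1.56 | 34%, shorter |
| 10% | 1.50 | 1.00 | 0.90 + 0.15 = 1.05 | 0.80 | 12%, shorter |

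Simulated trials (exponential rates, 800/400, censored at Day 90) agree: 12% to 14% longer in the first row and 33% to 38% shorter in the fourth.

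**Would a live-discharge analysis do better?** In simulation, with s = 20%, M = 0.75 and D = 1.10, the cause-specific ratio is 1.10 (significant in about 29%) and the subdistribution ratio 1.17 (about 62%), against 1.03 and 7% for the pooled test. Part of that 62% is mortality. With M = 0.75 and discharge unchanged, the subdistribution ratio is still about 1.09, significant in about 26% (1.05 and 13% at s = 10%). With discharge 5% slower it is still about 1.05, significant in about 11%. The cause-specific ratio has a different weakness: it can rise when sicker patients, who would have been discharged late, die sooner and leave the risk set.

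**The case against.** The outcome is called length of stay, not recovery. The plan defines it openly and consistently, and the cost analysis needs it. Three death analyses are planned (SAP 4.3.3 to 4.3.5), and the discharge curves are already in SAP 4.3.4. Exact cancellation needs a modest discharge gain. With discharge 20% faster, M = 0.75 and s = 20%, the pooled ratio is 0.96 + 0.15 = 1.11, which is diluted but not null (about 40% power). The rates are assumptions, and this is one of 15 listed secondary outcomes without multiplicity adjustment.

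Most of this stands, and it limits the point. A reader might infer that the pooled analysis is an error and should be replaced by live discharge. The documents do not support that: they set a bed-use outcome and analyse it as such. A reader might also infer that the pooling hides harm. It does not, because mortality is tested separately. Nor should the subdistribution p-value become the test of recovery: that ratio moves with mortality alone, as shown above, and it loses power when mortality is unchanged.

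What the objection does not answer is that the protocol attaches a hypothesis of benefit to a ratio whose direction is ambiguous, and that no planned estimate resolves it.

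**Conclusion.** The concern holds as a limit on interpretation. The pooled hazard ratio is a sound measure of time in hospital, but it cannot carry the benefit reading that Protocol 1.6 and 3.1 invite. Under the assumed constant rates and a 20% death share, a 25% lower death rate cancels a 6.25% faster discharge, and alone it gives about 0.95. A 50% higher death rate gives about 1.10, significantly shorter in roughly a third of trials. At a 10% share the effects are about half as large. The direction of the effect follows from the definition; its size depends on exit rates and a death share that the documents do not state. The primary test, sample size and stopping rule are unaffected. This is a cheap improvement.

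**What to change.** Keep the pooled analysis in SAP 4.3.7. Add a sentence there, with a matching one in Protocol 12.4.2, that it measures bed use, is not evidence of faster recovery, and that its direction is read beside the in-hospital death results.

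Add an analysis of discharge alive by Day 90 with in-hospital death as the competing event. Report the cause-specific hazard ratio and the subdistribution hazard ratio (or the difference in cumulative incidence), each with a 95% confidence interval, together with the SAP 4.3.4 curves. State that neither is read alone.

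State how transfers and palliative discharges are classified. Protocol 8.5 lists both to Day 30. Protocol 8.7 and 8.8 list home, local hospital or long-term care with no palliative category, and Protocol 8.9 records only death or discharge with its date. SAP 4.3.4 refers to discharge from the hospital of randomization, so the handling of transfers affects the result. Under the assumed rates about exp(−3) = 5% of control patients are still in hospital at Day 30, so few discharges fall after it.

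The cost is a few sentences and a few lines of code, since the date of death or discharge is already collected to Day 90. The downsides are one more unadjusted secondary estimate, and lower power for the subdistribution ratio than for the pooled test if mortality is unchanged: about 16% to 19% against 22% to 28% for 10% faster discharge.

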4.3.8. Need for Extra-Corporeal Membrane Oxygenation (ECMO)

The probability of requiring ECMO between randomization and Day 30 will be estimated for each treatment group by the proportion of individuals randomized to each group requiring ECMO between randomization and Day 30. The primary analysis will be based on a 2-sided Wald test of the null hypothesis that the probability of requiring ECMO is the same among individuals receiving CCP or standard of care. The percent relative risk reduction will be estimated along with a 95% confidence interval.

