4.3. Randomization Procedures

Patients will be randomized in a 2:1 ratio (CCP to standard of care). Patients will be randomized using a secure, concealed, computer-generated, web-accessed randomization sequence. Randomization will be stratified by centre and age (<60 and ≥ 60 years). Within each stratum, variable permuted block sizes will be used. This approach will ensure that concealment of the treatment sequence is maintained.

4.4. Intervention:

Patients will be assigned to the experimental treatment (CCP) or the control (standard of care).

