4.3.10. Myocarditis

The probability of developing myocarditis over the first 30 days will be estimated in a similar fashion to the way that the need for ECMO and renal replacement therapy are estimated and tests of effects will likewise be reported in a similar fashion.

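### The Wald test for ECMO and myocarditis has no rule for few or zero events and, in its usual unpooled form at 800:400, can signal false harm from CCP

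*SAP*

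**What the plan says.** SAP 4.3.8 estimates the probability of needing ECMO by Day 30 from the proportion in each arm. It then specifies: "The primary analysis will be based on a 2-sided Wald test of the null hypothesis that the probability of requiring ECMO is the same" in the two arms. The effect measure follows: "The percent relative risk reduction will be estimated along with a 95% confidence interval". SAP 4.3.9 repeats this wording for renal replacement therapy. SAP 4.3.10 carries it to myocarditis, where "tests of effects will likewise be reported in a similar fashion".

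Protocol 12.4.2 compares ECMO "based on a two-sided test of the difference between proportions" without naming Wald. For myocarditis it says: "The proportion of patients developing myocarditis over the first 30 days will be compared between the two arms based on a Wald test". The same section applies no multiplicity adjustment to secondary outcomes.

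Neither document states whether the Wald variance is pooled or unpooled, how the interval for the relative risk reduction is built, or what to do with a zero cell. Neither gives an exact alternative. Multiple imputation in SAP 4.1 deals with missing outcomes, not rare ones. No expected ECMO or myocarditis rate appears anywhere.

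**The concern.** A Wald test takes its standard error from the observed proportions. If the control arm has no events, it contributes nothing to that standard error. With x events on CCP and none on control, z is then close to √x, so four events are enough to pass 1.96.

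Under 2:1 allocation such a split is not unusual. If the treatments are equal and four events occur, the chance that all four fall in the CCP arm is about (2/3)⁴ = 0.20. The chance that all four fall in the control arm is about (1/3)⁴ = 0.01. The error therefore leans towards harm from CCP.

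Two things are at stake. A small chance imbalance in a cardiac or ECMO outcome could be reported as significant harm from plasma in an open-label trial. And the specified effect estimate might not exist, so that a substitute would be chosen after the counts were known.

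**Working it through.** **The plan's own figure.** SAP 1.3 assumes a 30% control risk and plans "to detect a relative risk reduction of 25% with CCP therapy using a 2-tailed test at level" 0.05 with 80% power. With 30% v 22.5% and 2:1 allocation, the average risk is (0.30 + 2 × 0.225)/3 = 0.25. The control-arm size is

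[1.96√(1.5 × 0.25 × 0.75) + 0.842√(0.30 × 0.70 + 0.225 × 0.775/2)]² / 0.075² ≈ 399,

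which rounds to 400 and gives 1200 in total. The figure reproduces, but it concerns the primary outcome only. It says nothing about rare secondary outcomes.

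**Inputs.** From the documents: 800 CCP and 400 control patients, two-sided 0.05 (2.5% per side), a Wald test, and a relative risk reduction defined as 100(1 − p_e/p_s) (SAP 4.2). Assumed: a true event rate equal in both arms, from 0.1% to 5% (1.2 to 60 expected events in 1200).

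**Method.** Exact enumeration: sum Bin(x; 800, p) × Bin(y; 400, p) over all pairs (x, y) where the test rejects, split by direction. With a = x/800, b = y/400 and m = (x + y)/1200:

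- Unpooled Wald: z = (a − b)/√[a(1−a)/800 + b(1−b)/400]
- Pooled z: z = (a − b)/√[m(1−m)(1/800 + 1/400)]

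Rejection rates under no effect, CCP worse / CCP better, in %:

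| True rate | Unpooled Wald | Unpooled total | Pooled z | Fisher exact | Mid-p |
|---|---|---|---|---|---|
| 0.1% | 0.6 / 0.04 | 0.6 | – | – | – |
| 0.25% | 5.2 / 0.4 | 5.6 | 0.04 / 4.2 | 0.01 / 1.7 | 0.04 / 1.6 |
| 0.5% | 7.9 / 1.0 | 8.9 | 0.7 / 3.3 | 0.3 / 2.6 | 0.7 / 2.3 |
| 1% | 4.8 / 1.3 | 6.1 | 1.9 / 2.8 | 1.3 / 2.4 | 1.9 / 2.5 |
| 2% | 4.1 / 1.6 | 5.6 | 2.3 / 2.8 | 1.7 / 2.1 | 2.3 / 2.4 |
| 5% | 3.3 / 1.8 | 5.2 | 2.2 / 2.7 | – | – |

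The unpooled CCP-worse error peaks at 8.1% (rate 0.43%) and the total at 9.0% (rate 0.45%). The total exceeds 6% only for rates of about 0.27% to 1.1%, or 3 to 13 expected events. With 600:600 the two tails are equal and at most about 2.5% at rates of 0.25% to 2%, so the skew comes from the 2:1 ratio.

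**Example, 4 v 0 events.** The difference is 4/800 = 0.005.

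- Unpooled: SE = √(0.005 × 0.995/800) = 0.00249, z = 2.01, p = 0.045.
- Pooled: m = 4/1200, SE = √(0.00333 × 0.99667 × 0.00375) = 0.00353, z = 1.42, p = 0.157.
- Fisher: p = 0.31.

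**Undefined estimate.** The relative risk reduction divides by the control proportion. The probability of no control event is (1 − p)⁴⁰⁰: 0.9975⁴⁰⁰ = 0.367, 0.995⁴⁰⁰ = 0.135 and 0.99⁴⁰⁰ = 0.018.

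**Ratio interval.** A log-relative-risk Wald interval excludes 1 in the CCP-worse direction in 0.1% of trials or fewer at rates up to 1%, with total error of 2.5% or less. It cannot be computed if either arm has no events: 45%, 15% and 1.8% of trials at 0.25%, 0.5% and 1%. It can also disagree with the test. With 10 v 1 events the unpooled Wald p is 0.032, but the relative risk is 5.0 with 95% CI 0.64 to 38.9.

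**The case against.** **The variance form is not stated.** The false-harm direction needs the unpooled difference. With pooled variance the lean reverses to false benefit. This stands as a limit on the claim. Unpooled is still the textbook meaning of a Wald test, it fits the protocol's difference of proportions for ECMO, and SAP 4.3.2 and 4.3.6 build their Wald tests from arm-specific standard errors. If the form is truly open, whether 4 v 0 counts as significant would depend on an unstated choice.

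**The rates are unknown.** Nothing in the documents places ECMO or myocarditis in the band where the inflation is material, and 0.5% lies close to the worst case. This also stands.

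**The problem would be visible.** At a 0.5% rate, false harm with no control events has probability 0.135 × P(at least 4 CCP events) = 0.135 × 0.567 = 0.076, so 7.6 of the 7.9 points would appear beside an inestimable effect. At 1% the same product is 0.018 × 0.958 = 0.017, only 1.7 of 4.8 points, so the warning is unreliable.

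**Stronger readings that fail.** A reader might infer that the ratio interval also generates false harm. It does not: it is conservative in that direction, and its defect is that it may not be computable. A reader might also infer that the plan will produce a harm signal, or that the main result or stopping is at risk. The outcomes are secondary, the primary test is separate, and Protocol 10.1 leaves stopping for harm to the IDSMC's judgement.

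**Conclusion.** The gap is real and of moderate importance. Two named secondary outcomes have a test and an effect measure that can both fail with few events, and the plan has no fallback. On the unpooled difference reading at 800:400, the CCP-worse error is roughly 1.6 to 3.1 times its nominal 2.5% at true rates of 0.25% to 2% (4.1/2.5 to 7.9/2.5). Overall inflation is confined to a narrower band: it is slight at 2% and absent at 0.1%. The relative risk reduction has a material chance of being undefined at rates of 0.5% or below.

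This rests on three assumptions: the unpooled form, equal true rates in the arms, and event rates that the documents do not supply.

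**What to change.** In SAP 4.3.8 and 4.3.10:

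- Specify Fisher's exact test, or its mid-p version, for ECMO and myocarditis whatever the observed counts, so that the data do not choose the test. Do the same for renal replacement therapy (SAP 4.3.9) if few events are expected.
- Do not substitute the pooled score z test. Under 2:1 it leans to false benefit: 4.2% CCP-better v 0.04% CCP-worse at a 0.25% rate, and 0 v 2 events gives p = 0.045 in favour of CCP.
- Report the risk difference with a score-based or exact 95% CI alongside the relative risk, and name the interval method for the relative risk.
- Report the risk difference alone when the control arm has no events.

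The cost is a few sentences, with no new data. The statistical price is conservatism. Fisher's total error is 1.7% to 3.8% at rates of 0.25% to 2%, and the loss is greatest in the harm direction (0.3% at a 0.5% rate). Mid-p is less conservative, at 1.7% to 4.6% in total, and neither exceeds 5% at the rates checked.
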